5.0 REGISTRATION PROCEDURES

5.1 General Guidelines

- 5.1.1 Eligible patients will be entered on study centrally at the Clinical Trials Support Unit in the Dan L. Duncan Comprehensive Cancer Center at the Baylor College of Medicine by the Study Coordinator. Coordinators at each facility will discuss eligibility with the study PI. Patient eligibility checklist must be completed prior to enrollment. Study consent must be obtained prior to performing any study related procedures.
- 5.1.2 Following Registration, patient should begin treatment within 30 days. Issues that would cause treatment delays should be discussed with the Principal Investigator.

5.2 Registration Process

- 5.2.1 Eligibility will be determined as per CTSU policy, according to the criteria in Section 4.
- 5.2.2 Eligible subjects will be registered into OnCore, and assigned a study ID number.
- 5.2.3 Issues that would cause treatment delays should be discussed with the Principal Investigator.
- 5.2.4 Filing of the signed consent form will be done per CTSU policy.

6.0 TREATMENT/INTERVENTION PLAN

6.1 Agent Administration

All patients will receive immediate release metformin in a pill form that allows for it to be crushed and administered via gastrostomy tube if necessary.

Metformin should be taken 60-90 minutes prior to a meal. The first dose of the day should be taken prior to administration of the daily radiation fraction. On days on

which the patient will undergo cisplatin infusion, metformin should be taken at least 90 minutes prior to cisplatin infusion.

The drug will be dispensed to the patient from the institutional pharmacy with appropriate self-administration instructions. The patients will be provided with a drug log and will be asked to provide the drug log on a weekly basis to the treating team in order to ascertain compliance with administration schedule and instructions.

Dose Level	Drug
DL -1	500 mg, PO, BID
DL 1	850 mg, PO, BID
DL 2	1500 mg, PO, BID

Phase I component:

All patients will undergo a 2 week “lead in” period in order to decrease the gastrointestinal toxicity associated with metformin. During this “lead-in” period, all patients will start metformin at the dose of 500mg PO BID. Dose increases to the targeted Dose levels are delineated in detail below. The start of radiation is Day 1.

The following modification is planned for the Phase I component. We will forgo escalation to Dose level 2 and proceed to the Phase II component using Dose level 1. The previous Dose level 2 information has been left in the protocol for the purpose of documentation (12/19/2018).

Dose level 1: 850mg per os (PO) twice daily (BID). All patients will start metformin 14 days (Day -14) (+/-24hr) prior to initiation of radiation at the starting dose of 500mg PO BID (administered prior to breakfast and prior to dinner), 7 days/week. On day -7 (+/-24hr), the dose will be escalated to 850mg PO BID for the first 3 patients enrolled in the phase I component. The dose of 850mg PO BID will then be continued for the entire duration of chemoradiation, administered 7 days/week. If the timing of radiation start is altered following metformin initiation patient may continue on the study as follows.

- If the timing of radiation is moved up (i.e. sooner than planned), the patient may continue the “lead in” phase as described above, and initiate the target Dose level once the “lead in” phase has been completed.
- If the timing of radiation start is delayed following the “lead in” phase, the patient will initiate the target Dose level once the “lead in” phase has been completed and continue taking metformin while waiting for radiation start.

Dose level 2: 1500mg per os (PO) twice daily (BID). All patients will start metformin 14 days (Day -14) (+/-24hr) prior to initiation of radiation at the starting dose of 500mg PO BID (administered prior to breakfast and prior to dinner), 7 days/week. On day -7 (+/-24hr), the dose will be escalated to 850mg PO BID. On day -4 (+/-24hr) the dose will again be escalated to 1500mg PO BID. Patients will then continue the 1500mg PO BID regimen for the entire duration of chemoradiation, administered 7days/week. If the timing of radiation start is altered following metformin initiation patient may continue on the study as follows.

- If the timing of radiation is moved up (i.e. sooner than planned), the patient may continue the “lead in” phase as described above, and initiate the target Dose level once the “lead in” phase has been completed.
- If the timing of radiation start is delayed following the “lead in” phase, the patient will initiate the target Dose level once the “lead in” phase has been completed and continue taking metformin while waiting for radiation start.

Dose level -1: 500 mg per os (PO) twice daily (BID). Although the 850mg PO BID dose is well within the current clinical range for metformin, the phase I component will also include a Dose level -1. If patients experience metformin related toxicity (see below) on the 850mg dose, we will de-escalate to a dose of 500mg PO BID. Patients will start metformin 14 days (Day -14) (+/-24hr) prior to initiation of radiation at the starting dose of 500mgPO BID (administered prior to breakfast and prior to dinner), 7days/week and continue at this dose for the entire treatment course. This dose will then be utilized for the entire phase I component of the trial. All patients will receive immediate release metformin in a pill form that allows for it to be crushed and administered via gastrostomy tube if necessary. If the timing of radiation start is altered following metformin initiation patient may continue on the study as follows.

- If the timing of radiation is moved up (i.e. sooner than planned), the patient may continue the “lead in” phase as described above, and initiate the target Dose level once the “lead in” phase has been completed.
- If the timing of radiation start is delayed following the “lead in” phase, the patient will initiate the target Dose level once the “lead in” phase has been completed and continue taking metformin while waiting for radiation start.

Determination regarding maximum tolerated dose (MTD) for the phase I component will be performed as described. See section 7.2 specific metformin evaluable toxicities and dose limiting toxicities (DLTs). All patients who are enrolled and receive the study drug will be evaluated for toxicity, but only patients which complete $\geq 70\%$ of the total planned study drug dose to be administered during the standard of care radiation treatment period will be used to ascertain absence of DLT as part of the Phase I component and planned escalation strategy detailed in the table in section 13.2.

Assignment of patients to a Dose levels will be performed by the PI or one of the co-investigators listed on the protocol if the PI is not immediately available. Study coordinators will not be expected to assign patients to Dose levels. All decisions regarding dose escalation or dose reduction will be made by the PI or one of the co-investigators listed on the protocol if the PI is not immediately available, using the general schema listed above and the toxicity driven modifications listed in Section 7. Modifications to the standard of care treatment consisting of chemotherapy and radiation will be made by the treating physicians, per standard clinical practice.

Phase II component:

All patients used for evaluation of the phase II component will be treated using one of the Dose levels determined by the process described in section 13.2. To be evaluable for response patients must have taken $\geq 70\%$ of the total metformin dose to be administered during the standard of care radiation treatment period. Regardless of the determined MTD, all patients will start with a 1 week “lead-in” period of 500mg PO BID. If the timing of radiation start is altered following metformin initiation patient may continue on the study as follows. If the timing of radiation is moved up, the patient may continue the “lead in” phase as described above, and initiate the target Dose level once the “lead in” phase has been completed. If the timing of radiation start is delayed following the “lead in” phase, the patient will initiate the target Dose level once the “lead in” phase has been completed and continue taking metformin while waiting for radiation start.

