12.1.1. Definitions

Evaluable for toxicity. All patients will be evaluable for toxicity from the time of their first treatment with metformin until 30 days following treatment completion.

Evaluable for objective response. All patients included in the study must be assessed for response to treatment, even if there are major protocol

treatment deviations. These patients will have their response classified according to the definitions stated below.

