A response rate $\geq 60\%$ would be considered effective for patients undergoing metformin plus standard of care, while a response rate $\leq 40\%$ is not considered as effective. The phase II portion of the trial would require at least 28 evaluable patients treated at the MTD. For the purposes of this study, a response will be defined as overall complete response (CR) or overall partial response (PR) (see Table in section 12.1.4.3). Stable disease or progressive disease will be defined as a non-response. The criterion for significance (alpha) has been set at 0.10. The test is 1-tailed, which means that an effect in one direction (improvement) is expected and will be interpreted. Calculation are based on the assumptions of uniform accrual over time. With the proposed sample size of 28 patients the study will have power of 80% to yield a statistically significant result. The treatment strategy (metformin plus standard of care) is considered effective if 17 or more responses are observed among the 28 patients.

Total study sample size.

This study will enroll at least 3 patients at each dose level and at least 28 patients at the MTD level. Participants will continue to be enrolled and monitored for toxicity according to the rules specified above until 28 efficacy evaluable participants have been enrolled to any single dose level. For the purposes of this analysis, a subject is considered evaluable for the primary endpoint after completing at least one dose of Metformin. It is expected that all dose levels will be safe and assuming that even the highest dose level has a DLT rate substantially lower than the target (i.e. $<10\%$), which is what we expect, we will have more than 99% chance of selecting the top dose level at the end of the trial. In this case the total number of patients enrolled would be 31 (3+28). Retrospective clinical studies have not demonstrated an increase in treatment toxicity for patients undergoing cisplatin for HNSCC while taking metformin. It is anticipated that 1-2 patients per month

will be accrued to the study. Depending on the toxicity, this will allow for completion of study within 33-39 months of study initiation.

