13.5 Reporting and Exclusions

13.5.1 Evaluation of toxicity. All patients will be evaluable for toxicity from the time of their first treatment with metformin.

13.5.2 Evaluation of response. All patients included in the study must be assessed for response to treatment, even if there are major protocol treatment deviations. Each patient will be assigned one of the following categories:

1) complete response, 2) partial response, 3) stable disease, 4) progressive disease, 5) early death from malignant disease, 6) early death from toxicity, 7) early death because of other cause, or 9) unknown (not assessable, insufficient data). [Note: By arbitrary convention, category 9 usually designates the “unknown” status of any type of data in a clinical database.] All of the patients who met the eligibility criteria (with the possible exception of those who received no study medication) should be included in the main analysis of the response rate. Patients in response categories 4-9 should be considered to have a treatment failure (disease progression). Thus, an incorrect treatment schedule or drug administration does not result in exclusion from the analysis of the response rate. Precise definitions for categories 4-9 will be protocol specific.

All conclusions should be based on all eligible patients. Subanalyses may then be performed on the basis of a subset of patients, excluding those for whom major protocol deviations have been identified (e.g., early death due to other reasons, early discontinuation of treatment, major protocol violations, etc.). However, these subanalyses may not serve as the basis for drawing conclusions concerning treatment efficacy, and the reasons for excluding patients from the analysis should be clearly reported. The 95%

confidence intervals should also be provided.

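### Section 6.1 makes phase II patients evaluable for response only at 70% or more of the metformin dose, which contradicts sections 13.2 and 13.5.2, and no sentence reconciles them

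*Combined protocol and SAP*

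**What the plan says.** - **Section 6.1, phase II paragraph.** "To be evaluable for response patients must have taken" at least 70% of the total metformin to be given during the radiation period. The paragraph cites 13.2 only for the choice of dose level. A separate phase I sentence in 6.1 also uses 70%, but to decide which patients can show absence of DLT.
- **Section 13.2.** Enrolment continues "until 28 efficacy evaluable participants have been enrolled to any single dose level". The next sentence reads: "For the purposes of this analysis, a subject is considered evaluable for the primary endpoint after completing at least one dose of Metformin". The treatment "is considered effective if 17 or more responses are observed among the 28 patients".
- **Section 12.1.1.** "Evaluable for objective response. All patients included in the study must be assessed for response to treatment", even with major protocol deviations. It says nothing about who counts as a failure or about subsets.
- **Section 13.5.2.** The main response analysis takes all eligible patients, possibly excepting those who received no study drug. It adds that "an incorrect treatment schedule or drug administration does not result in exclusion from the analysis of the response rate". Response categories 4-9 (progression, early death, unknown) count as failures. "All conclusions should be based on all eligible patients". Subsets that exclude major deviations are allowed, but "these subanalyses may not serve as the basis for drawing conclusions concerning treatment efficacy".

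**The concern.** Sections 6.1 and 13.2 both define who is evaluable for the phase II response, and they give different sets. No sentence labels the 70% set as secondary or says which section governs.

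The primary result is a count of responders against a fixed threshold, so the definition can change the result. Dropping patients for low exposure is also not neutral. Section 7.2.3 stops metformin for progression, for toxicity that cannot be improved and when radiation is terminated early. Such patients, and early deaths, can fall below 70%. Section 6.1 would remove them, whereas 13.5.2 keeps them, with progression and early death counted as failures.

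A site or analyst counting evaluable patients from 6.1 would close accrual at a different point, and analyse different patients, from one working from section 13.

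**Working it through.** **Inputs from section 13.2.** Response rates 40% (not effective) and 60% (effective), one-sided alpha 0.10, power 80%, 28 patients, success at 17 or more responses.

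**The plan's own figures.** The normal approximation gives n = [(1.2816 + 0.8416) × √0.24 / 0.20]² = 27.05, so 28 reproduces. The printed rule does not. With X ~ Bin(28, p), P(X ≥ 17) is 0.0215 at p = 0.40 and 0.551 at p = 0.60, against the stated 0.10 and 80%. That mismatch is a separate matter. Here 0.0215 and 0.551 serve only as the baseline for the rule as printed.

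**Reading A: 6.1 governs accrual, so enrolment runs to 28 patients at 70% or more.** Let f be the share of treated patients below 70% and q their response rate. Both are assumptions. If the all-treated rate is 40%, the rate among those kept is p = (0.40 − f·q)/(1 − f). For example, f = 0.20 and q = 0.20 give p = (0.40 − 0.04)/0.80 = 0.45. P(X ≥ 17 of 28) is then:

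| f | q = 0 | q = 0.10 | q = 0.20 | q = 0.30 | q = 0.40 |
|---|---|---|---|---|---|
| 10% | 0.062 | 0.049 | 0.038 | 0.029 | 0.022 |
| 20% | 0.172 | 0.113 | 0.070 | 0.040 | 0.022 |
| 30% | 0.428 | 0.261 | 0.136 | 0.060 | 0.022 |

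The probability reaches 0.10 at p = 0.4684. Solving f = (0.4684 − 0.40)/(0.4684 − q) gives 14.6% excluded for q = 0, 18.6% for q = 0.10, 25.5% for q = 0.20 and 40.6% for q = 0.30.

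**Reading B, a hybrid: accrual by 13.2 (28 treated), analysis by 6.1, threshold still 17.** With k excluded and a true all-treated rate of 60%, X ~ Bin(28 − k, p), where p = (0.60 − (k/28)·q)/(1 − k/28). The chance of success, from a baseline of 0.551, is:

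| k | q = 0.60 | q = 0.20 | q = 0 |
|---|---|---|---|
| 3 | 0.274 | 0.458 | 0.560 |
| 6 | 0.072 | 0.347 | 0.577 |

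**Can a patient managed as the protocol directs fall below 70%?** There are two routes, apart from the stopping rules.
- *Creatinine hold (7.2.4).* Metformin is held for a week and then for as long as creatinine stays raised. If doses are otherwise full, a hold of more than 30% of the radiation period is enough: 0.30 × 6.5 = 1.95 weeks, or 0.30 × 7 = 2.1 weeks.
- *Dose reduction (7.2.1 table, 7.2.2).* A patient who cannot re-escalate stays on the highest tolerable dose. With the 850 mg BID level named in the 12/19/2018 note in 6.1 as the denominator, the next step is 500/850 = 58.8%. The total falls below 70% after 0.30/0.412 = 73% of the period at 500 mg, which is 4.7 of 6.5 weeks or 5.1 of 7 weeks. If the denominator is instead the dose as prescribed after permitted changes, this route closes. The phase II wording does not say which is meant.

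**The case against.** The strongest reply is that section 13 already decides the matter. The one-dose definition directly follows the 28-patient accrual rule, and 13.5.2 forbids exclusion for drug-administration deviations and bars efficacy conclusions from subsets. The projected total of 31 (3 + 28) also leaves no room to replace patients below 70%. On that view, 6.1 contains one stray sentence in a drug-administration section. Most of this stands, and it limits the risk. It does not remove the contradiction, because 6.1 states its condition as a requirement and nothing subordinates it.

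Three stronger readings are tempting, and the documents do not support them.
- *That the primary set is undefined, or that the trial plans a per-protocol primary analysis.* Section 13 defines the set, and applying 6.1 would breach 13.5.2.
- *That the false-positive rate exceeds 0.10.* On the printed rule this needs roughly 15% excluded with no responders, or a quarter excluded responding at 20%. Response rates near zero are plausible mainly for progression, early death or terminated radiation. Patients who stop only for metformin toxicity can still complete chemoradiation and respond.
- *That power collapses.* Reading B needs one section's definition for accrual and the other's for analysis. If either section is followed throughout, accrual reaches 28 evaluable patients.

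Nor do the documents say how often a creatinine hold or a lasting dose reduction would take a patient below 70%.

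**Conclusion.** The point holds as an unreconciled contradiction that should be fixed. Section 6.1 gives a rule for the response denominator that conflicts with 13.2 and 13.5.2 and, if followed, removes patients partly because of their outcome.

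If 6.1 governed accrual and the true all-treated rate were 40%, the chance of declaring the treatment effective would rise from 0.022 to 0.038-0.062 with 10% excluded, 0.070-0.17 with 20%, or 0.14-0.43 with 30%, for excluded patients responding at 20% down to 0%. It would not change if they responded at 40%. The share excluded and its response rate are assumptions, and the upper figures are extremes.

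The loss of power (0.55 to 0.27 with three excluded who respond at 60%) arises only under the hybrid reading, and it disappears if the excluded patients would not have responded.

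**What to change.** In the phase II paragraph of 6.1, replace the 70% condition with a reference to 13.2 and 13.5.2. Leave the phase I 70% rule for absence of DLT as it is.

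State once in 13.2 that:
- the primary set is all eligible patients at the phase II dose who took at least one dose of metformin;
- early death, progression and unassessable patients count as non-responders, as 13.5.2 already provides;
- no patient is replaced for low metformin exposure, early stopping or a missing assessment;
- a treated patient later found ineligible does not count toward the 28, so accrual continues to 28 eligible treated patients. Without this, the set could fall short of 28 against a threshold of 17.

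Report any 70% set only as a labelled sub-analysis that cannot support the efficacy conclusion, and say whether its denominator is the target dose or the dose as modified.

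The cost is an edited clause in 6.1 and a short statement in 13.2, with no new data or assessments. A late finding of ineligibility could add a patient. The response rate may be slightly less favourable and will include patients with little metformin exposure, whom the sub-analysis can show separately.

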6.2 Other Modality(ies) or Procedures

Chemotherapy: Weekly cisplatin will be administered at the discretion of the treating physicians. Below is a suggested regimen for administration that is recommended in order to standardize administration and treatment of side effects. Deviations from this regimen are allowed, but should be documented by the treating physician. It is recommended that cisplatin be infused over 60 minutes intravenously at 40 mg/m² weekly, starting on week 1 day 1 of radiation, for a maximum of 7 weeks. Cisplatin can be given either before or after the radiation therapy fraction that is given on the same day. If radiation is held for more than 2 days (for any reason), cisplatin may be held as well until radiation resumes. The administration of cisplatin should follow the standard anti-emetic premedication and hydration as follows: Ondansetron 16mg + Dexamethasone 8 mg should be infused 30 minutes prior to cisplatin infusion. Normal saline 1000 mL + KCl 20 mEq / L + 1 gm MgSO₄ will be infused over 2 hours prior to administration of cisplatin. Normal saline 500ml should be infused after completion of cisplatin. Any pre-existing dehydration should be corrected prior to cisplatin administration. Should extravasation occur, the treating physician should follow institutional guidelines for additional management. Breakthrough nausea and vomiting should be managed at the discretion of the medical oncologist or radiation oncologist. Delayed nausea and vomiting (greater than 24 hours after chemotherapy)

administration) may be managed by the addition of aprepitant concurrently or with metoclopramide and dexamethasone. Potential delayed nausea regimens include:

1. The NK-1 antagonist, aprepitant (125 mg p.o.), may be added for prevention of delayed emesis on the day of cisplatin administration and for two consecutive days thereafter (80, 80), with a corticosteroid, such as dexamethasone on days 1-4. Fosaprepitant 115 mg iv may be substituted for the aprepitant 125 mg on day 1. Dexamethasone should be reduced on day 1 to 12 mg and delivered at up to 8 mg total daily for the 3 days following cisplatin administration. A 5HT3 antagonist (e.g. granisetron, ondansetron) may be also given for the 3 days following cisplatin administration, only if palonosetron was not given prior to chemotherapy.
2. Delayed emesis also may be managed by the addition of dexamethasone 8 mg bid x 2 days, followed by dexamethasone 4mg bid x 2 days, beginning on the day after chemotherapy; and oral metoclopramide 0.5 mg/kg (usually 20-40 mg) qid x 2-4 days. A 5HT3 antagonist (e.g. granisetron, ondansetron) may also be given for up to 3 days after cisplatin.

External beam radiotherapy (EBRT): EBRT will be administered at the discretion of the treating physician as deemed appropriate for the individual patient and tumor characteristics. Below is a suggested regimen for administration that is recommended in order to standardize administration and treatment of side effects. Deviations from this regimen are allowed, but should be documented by the treating physician. For oral cavity and oropharynx primary tumors, the prescribed radiotherapy dose will be 69.96 Gy in 2.12 Gy once-daily fraction size (total of 33 fractions). For larynx and hypopharynx tumors primary tumors, the prescribed radiotherapy dose will be 70 Gy in 2 Gy once-daily fraction size (total of 35 fractions). The daily dose of 2.12 Gy will be prescribed such that 95% of the PTV69.96 volume receives 69.96 Gy. Radiotherapy should begin on a Monday, Tuesday or Wednesday. Treatment breaks must be clearly indicated in the treatment record along with the reason(s) for the treatment break(s). Treatment breaks should be allowed only for resolution of severe acute toxicity and/or for inter-current illness and not for social or logistical reasons. Any treatment break(s) exceeding 2 treatment days for reasons other than toxicity/illness will be considered a protocol deviation. Missed treatments due to holidays or for logistic reasons can be compensated for by delivering an additional treatment (BID, two fractions in one day at least 6 hours apart) during the week, or treating on the Saturday or Sunday of that week, or adding to the end of treatment. IMRT will be utilized for treatment planning, and planning will consist of a single plan utilizing a simultaneous integrated boost (SIB) technique as outlined below. Daily image-guidance in the form of cone-beam CT is required to ensure accurate daily set-up and reproducibility.

Target and Normal Tissue Volume Definitions For Oral Cavity and Oropharynx
CTV69.96: This volume will receive 2.12 Gy per day in 33 fractions over 6.5 weeks. CTV69.96 consists of the primary tumor and grossly involved

lymphadenopathy with a 0.5 cm expansion of the gross tumor volume (GTV) to cover potential local invasion. A 0.3 cm expansion to CTV69.96 will be utilized to create PTV69.96. CTV63 will receive 1.91 Gy in 33 fractions and consists of intermediate-risk disease sites and is defined as a 1 cm expansion on the GTVs along with the remainder of neck levels with grossly involved disease (i.e. left level II with a grossly involved left level II node). Additionally, it includes anatomical patterns of microscopic spread defined at the discretion of the treating radiation oncologist. A 0.3 cm expansion to CTV63 will be utilized to create PTV63. CTV57 will receive 1.73 Gy per day in 33 fractions and consists of low-risk sub-clinical disease sites, including the uninvolved contralateral neck, and uninvolved ipsilateral low neck. A 0.3 cm expansion to CTV57 will be utilized to create PTV57.

Target and Normal Tissue Volume Definitions For Larynx and Hypopharynx
CTV70: This volume will receive 2.0 Gy per day in 35 fractions over 7 weeks. CTV70 consists of the primary tumor and grossly involved lymphadenopathy with a 0.5 cm expansion of the gross tumor volume (GTV) to cover potential local invasion. A 0.3 cm expansion to CTV70 will be utilized to create PTV70. CTV63 will receive 1.8 Gy in 35 fractions and consists of intermediate-risk disease sites and is defined as a 1 cm expansion on the GTVs along with the remainder of neck levels with grossly involved disease (i.e. left level II with a grossly involved left level II node). Additionally, it includes anatomical patterns of microscopic spread defined at the discretion of the treating radiation oncologist. A 0.3 cm expansion to CTV63 will be utilized to create PTV63. CTV57 will receive 1.63 Gy per day in 35 fractions and consists of low-risk sub-clinical disease sites, including the uninvolved contralateral neck, and uninvolved ipsilateral low neck. A 0.3 cm expansion to CTV57 will be utilized to create PTV57.

Radiation Treatment Related Toxicity

Grade 3 therapy-induced mucositis and/or dysphagia are expected to develop in about one third to two thirds of patients. Nutritional evaluation prior to the initiation of therapy for a prophylactic gastrostomy (PEG) tube placement is recommended. Other common radiation adverse events include: fatigue, weight loss, regional alopecia, xerostomia, hoarseness, transient ear discomfort, dysgeusia, and skin erythema and desquamation within the treatment fields. These side effects vary in intensity and are typically managed during the weekly visit with the treating radiation oncologist. Less common long-term treatment adverse events include: hypothyroidism, loss of hearing, chronic swallowing dysfunction requiring permanent feeding tube, and cervical fibrosis. Much less common radiation adverse events include: mandibular osteoradionecrosis (<5% incidence with proper pre-therapy dental evaluation), and cervical myelopathy (<1% with restriction of spinal cord dose to ≤ 45 Gy).

